6.4 Informed consent

Potential participants will be told about the trial by their clinicians, or, if they have accepted to hear about research opportunities, we will contact potentially eligible participants by phone, letter or at a memory clinic appointment, to ask whether they would be interested in participating. If the potential participant agrees to hear about the trial, we will send them a participant information sheet. If there is a communication partner involved who would also be happy to participate, we will also send them an information sheet. Following this, we will contact the participant and their communication partner within 48-72 hours to answer any questions they may have about the trial and confirm whether or not they wish to take part.

It is the responsibility of the Investigator, or a person delegated by the Investigator to obtain written informed consent from each participant prior to participation in the trial, following adequate explanation of the aims, methods, anticipated benefits and potential hazards of the trial. Participant consent will be obtained at the screening visit before any procedures. The research assistant will have been GCP trained, and will have received specific training in consent for research purposes provided by the trial team, and they will have been delegated this duty by the CI on the Staff Signature and Delegation of Tasks (delegation log). All researchers will adhere to the respective Trust policies for home visits.

Some potential participants may have physical disabilities that render them unable to initial the consent form. These participants may use ticks instead of initials in the consent form. Potential participants may also be physically unable to sign the consent form. These participants may use a mark or tick instead of

signature. If these alternate forms of consent are used, the researcher taking consent will document the rationale for this in the trial documentation. This procedure is consistent with HRA guidance³.

The Investigator or designee will explain that participants are under no obligation to enter the trial and that they can withdraw at any time during the trial, without having to give a reason. No trial procedures will be conducted prior to the participant giving consent by signing the consent form. Consent will not denote enrolment into trial. A copy of the signed consent form will be given to the participant. The original signed form will be retained in the trial master file at site and a copy placed in the medical notes. The PIS and consent form will be reviewed and updated if necessary throughout the trial (e.g. where new safety information becomes available) and participants will be re-consented as appropriate.

Potential participants lacking capacity will be excluded. However, as the participants of this trial will have been diagnosed with MCI, we do not expect them to lack capacity. As the trial progresses, we will continue to assess their capacity on an ongoing basis at each visit. All members of the research team with participant contact are GCP-trained and will be trained in the assessment of capacity, including for research participation. Any doubts about capacity will be discussed with the CI.

For the Remote Hearing Intervention sub-study (during COVID-19), we will approach TACT participants as per sections 6.1-6.3 above. Those who agree to consider participation in the RHI sub-study will be posted a Participant Information Sheet & consent form (the consent form is for their reference, but consent will be taken verbally over the telephone). After 48h for consideration, researchers will call these participants to discuss and answer any questions, and take recorded consent over the telephone (expected duration 45-60 minutes total). This consent will be recorded with the participants' permission.

7 Product/Interventions

7.1 Name and description of intervention(s) under investigation

The Hearing Intervention

Motivation for the intervention. A key difficulty in delivering a trial of hearing aids to prevent dementia arises from the expected low adherence to hearing aid use in standard audiological care. Currently less than one in three people with hearing loss in the UK are prescribed hearing aids, and, of those who start using them, up to half of them do not use them consistently or abandon them altogether. Lack of adherence to hearing aids is also more prevalent in those with MCI, as poorer cognition is a risk factor for non-use of hearing aids in those with hearing loss. With optimal fitting and post-fitting support, long-term adherence to hearing aid use can exceed 80% as shown by population-based survey data in Switzerland [17] and as demonstrated in the pilot of the ACHIEVE study [18].

We have conducted preparatory qualitative and feasibility studies, in which we identified several obstacles for hearing aid use in people with MCI and mild dementia. Our qualitative interviews established that people with MCI have additional difficulties to the rest of the population in hearing aid use linked to their cognitive impairment, often forgetting they have them or where they are. We also tested the hearing of 17 people recently diagnosed with MCI, and found that 12 of them (70.5%) had untreated hearing loss. We reported these findings to their GPs, and found that, after three months, only three participants had been assessed by audiology, and of those, only two participants had been prescribed hearing aids, with both of them reporting difficulties using them and declining time of use (less than four hours).

³ <http://www.hra-decisiontools.org.uk/consent/principles-general.html>

The conclusion from this preparatory work is that using routine NHS pathways for audiological assessment and hearing aid prescription would not be an effective option for the trial as most participants would remain untreated. Our work has also shown that even if prescribed, many people are likely to abandon hearing aid use if we only provide them with routine, clinic-based NHS care. Low adherence to hearing aids would make a trial unfeasible. We have therefore developed the Hearing Intervention to provide hearing aid treatment and support hearing aid use in people with MCI.

Intervention components. The Hearing Intervention is a manualised intervention which assesses, treats and supports people in their own home so they remain adherent to hearing aid use. The Hearing Intervention adapts the best practices hearing intervention of the ACHIEVE trial (which is clinic-based) to address the additional memory-related obstacles to hearing aid use that we expect in the MCI population. The Hearing Intervention also incorporates the British Society of Audiology best practices guidelines for use in a British context. The intervention consists of hearing aid provision, as well as a series of one-to-one home visits with our researchers to: identify and address the participants' individualised hearing needs; provide training and practical support to use the hearing aids effectively; and provide reminders and cues to hearing aid use that can be integrated into the person's daily routine.

Based on current evidence and our previous work in people with MCI we have modified the ACHIEVE intervention. These modifications have included an added emphasis on training, repetition and simplification of information, simplification of trial procedures as well as adapting these procedures to a home-based intervention. The intervention emphasis will evolve throughout the intervention, with a shifting focus from motivation and planning in hearing aid pre-fitting and fitting meetings, and towards coping, monitoring and support after fitting. A model of the intervention and its components is presented in Figure 2.

[figure not shown]

Figure 2. Prototype of the intervention to support hearing aids use. The cognitive processes that lead to the participant deciding to start to use hearing aids and persist with them (in red) are reinforced by the different components of the intervention (blue and light grey). Carers will be included as part of the intervention whenever possible. The Health Action Process

Approach framework, HAPA, is adapted from Schwarzer, 2008 [19].

The intervention will be delivered at the participants' homes to facilitate engagement and reduce anxiety, by a research audiologist in combination with a graduate psychologist research assistant. The intervention will be manualised to facilitate standardisation and scalability, but will also be individualised according to the individual's needs and circumstances. If available, a communication partner will participate in the intervention.

Further details on our intervention are provided in section 8.3 of this document (page 34).

The Remote Hearing Intervention (RHI)

The RHI will attempt to replicate the Hearing Intervention during COVID-19, where contact with participants needs to be avoided as it would carry the risk of spreading the virus. Participants will be provided with the hearing aids and an adapted toolkit, factsheet, calendar sheets and DVD of video clips on hearing aids operation and management (Figure 3). This will be remotely supported by the study team, including programmed contact and, if required, troubleshooting by the audiologist. Remote contact will also be used by the researchers to remind participants to wear their hearing aids and promote hearing aid use.

The Healthy Ageing Intervention

From the point of view of hearing care, the Healthy Ageing Intervention will be a control intervention, with audiological treatment as usual provided, whereby participants will be told that the trial assessment has identified a potentially treatable hearing loss, and they will be encouraged to contact their GP and discuss treatment options.

The purpose of this control arm is to judge the acceptability of being randomised after confirmation of hearing impairment, so that we know the feasibility of moving to a full scale trial. Ethical reasons preclude a trial using a non-intervention arm that would deny hearing treatment to people who need it. Therefore, participants in this arm will have the results of their audiological assessment communicated to them with advice to visit their GP should they wish to seek NHS audiological treatment. Based on previous published evidence of poor take-up and low adherence to hearing aids, as well as our own preparatory work, we expect participants in the control arm to obtain and adhere to hearing aids at a very low rate, and sufficiently low to provide a meaningful comparison with participants in the Hearing Intervention, where we expect high hearing aid adherence.

Audiological services in the UK aim to provide treatment (usually a hearing aid) within 18 weeks of GP referral. In London, the median waiting time between referral and treatment is 3.3 weeks, with 97% of patients receiving treatment within 18 weeks, according to recent figures (NHS England, December 2017). Therefore the trial duration (6 months) should allow sufficient time for hearing aid fitting in the Healthy Ageing Intervention arm should the participant wish to pursue this treatment. We will consent participants so we can review GP notes and audiology clinical records as to whether a referral for audiological assessment was made and whether hearing aids were prescribed. NHS-prescribed hearing aids currently have data-logging capabilities, so that objective information on hearing aid use can be obtained from users in the Healthy Ageing Intervention arm as well as in the Hearing Intervention arm. The proportion of people in the Healthy Ageing Intervention arm who will be prescribed hearing aids and the degree to which they will adhere to this treatment when no adherence support is provided are necessary numbers for the planning of the future trial. In the control arm, we expect prescription of hearing aids and compliance to be very low based on previous evidence.

Social contact may be an important element in preventing progression to dementia. The Hearing Intervention as part of the TACT trial is an intensive intervention, involving several one-to-one sessions between the participant and a researcher. The control arm intervention (Healthy Ageing) will therefore be matched to the Hearing Intervention in terms of social contact with researchers. During these matched face-to-face sessions, the researchers will be delivering a Healthy Ageing Intervention of health education on different topics targeting areas of behavioural change acting on several risk factors that have been linked to progression from MCI to dementia. The Healthy Ageing Intervention is based on the ACHIEVE equivalent intervention [18, 20] with modifications for the UK context and

NHS guidance. These topics are delivered as manualised one-to-one sessions with a researcher, focusing on a risk factor at a time. The intervention is manualised, and the researchers delivering the intervention will be certified using existing online training. The topics used in the Healthy Ageing Intervention in this trial will include:

- Lower systolic blood pressure
- Eat a healthy diet
- Be physically active
- Maintain healthy bones, joints and muscles

7.2 Storage and handling of drug at site (if applicable) N/A

7.3 Accountability of drug (if applicable) N/A

7.4 Concomitant medication (if applicable) N/A

7.5 Dosages, modifications and method of administration (if applicable) N/A

8 Trial procedures

8.1 Pre-intervention assessments

Screening visit (Visit 0, day 0)

The screening visit will be conducted by an audiologist (Aud) and research assistant (RA).

The following trial procedures will be conducted at the screening visit (Visit 0):

- Consent of participant, and, if applicable, of communication partner (RA)
- Assessment of non-audiological eligibility criteria: confirm that criteria are met with regards to age, English command, willingness to be randomised and comply with trial procedures (RA)
- If the participant is eligible, then administration of hearing screening: Hearcheck and Shoebox audiometry (RA)
- Measurement of ambient noise (sound level meter), with remedial measures taken if ambient noise greater than 50 A-weighted decibel dB(A) (Aud)
- Interview and assessment by research audiologist, audiological medical history, visual inspection, otoscopy, tympanometry, pure tone audiometry (air conduction (with Audiocups), bone conduction & masking), tuning fork test (if required), phoneme recognition in quiet, speech in noise (QuickSIN); to assess audiological eligibility criteria (Aud)
- if individual meets all the inclusion criteria, inclusive of audiometric eligibility criteria, as per section 6.1 and 6.2: randomisation (Aud)

- if randomised to hearing intervention: evaluation of optimal hearing aid type (based on audiometric test results, physical appearance of outer ear, and manual dexterity); decision on earmold or receiver-in-canal (RIC). If earmold then take impression at end of visit (Aud)
- if hearing loss is detected, the research audiologist will inform the participant's GP of the results of the hearing test

The screening visit can be administered over two sessions on different days if required. The assessment will be timed by the RA, as one of the objectives of the trial is to assess tolerability of the schedule of assessments, with 2 hours considered the maximum tolerable for frail older adults. If the assessment goes beyond two hours, or if the participant requests a break or is showing signs of fatigue in the opinion of the researcher, the researcher will offer scheduling another meeting within 2 weeks to finalise the testing.

Baseline visit (Visit 1)

The baseline visit will be conducted by an RA.

Purpose: to gather baseline measures of primary and secondary outcomes.

When: Day 0 to 2 weeks after screening (V0) and 1-2 weeks before first intervention visit (V2).

The following trial procedures will be conducted at baseline visit (V1) with participant:

- obtain demographic information
- obtain medical history, including history of falls, and current medication
- Procedure to verify that participant can adequately hear instructions from tester and stimuli of the battery
- administer neurocognitive battery
 - o Speech audibility procedure (ensuring speech understanding for tests)
 - o Delayed word recall test (DWRT): encoding [23]
 - o Addenbrooke Cognitive Examination (ACE-III) [22]
 - o Trail Making Test (TMT) Part A and B [25]
 - o Delayed word recall test (DWRT): recall
- Self-reported hearing disability - Hearing Handicap Inventory for the Elderly – Screening version (HHIE-S) [27]
- Geriatric depression scale (GDS) [28]
- Quality of life questionnaires
 - o Short Form 36 [29]
 - o EQ-5D [30]
- Items of the Lawton – Brody Instrumental Activities Of Daily Living Scale (I.A.D.L.): rated by RA based on self-report. Items: A. Telephone, F. Transport, G. Medication, H. Finances as those are the most predictive of future progression to dementia [31]
- Social function scale SF-DEM – patient rated version [32]
- UCLA Version 3 Loneliness Scale [33]
- Grip strength
- Fitting of accelerometer

If communication partner is present, the following procedures will be conducted:

- Consent of communication partner (if not done at screening visit – V0)
- Demographic data for communication partner

- Quality of their communication with the participant and HL impact: The Hearing Impairment Impact–Significant Other Profile
- Health-related quality of life of communication partner: SF36 and EQ-5D
- Hospital anxiety and depression HADS34], validated in caregiver population
- Proxy information on participant:
 - o Carer-rated version of the SF-DEM [32].
 - o Four-items (A,F,G,H) of Lawton – Brody Instrumental Activities Of Daily Living Scale

The assessment will be timed by the RA. If the assessment goes beyond two hours, or if the participant requests an adjournment at any time or are showing signs of tiredness in the opinion of the researcher, the researcher will offer scheduling another meeting within 2 weeks.

All pre-treatment procedures will be carried out as specified in the schedule of assessments (appendix 1). Given that many of the participants will be older adults with poor memory and with some risk of experiencing health difficulties, it may not be possible to complete the visits within the scheduled time then a delay is permitted. There are no cut-off times, rather, every effort should be made for the participant to complete the necessary visits within schedule. Reasons for delays or deviations from the allocated schedule will be recorded.

Pre-intervention procedures for RHI sub-study (during COVID-19)

After consent, participants' baseline outcome measures will be obtained through remote interview. These will include a simplified version of the above battery to include:

- Collection of medical or audiological history, or update on any changes in medical or audiological history since TACT baseline visit if applicable (when this information was initially collected)
- Mood: Geriatric depression scale (GDS) [28]
- Cognition: Addenbrooke Cognitive Examination (ACE-III) [22]; these will include only those items that can be obtained by remote assessment
- Hearing: Personalised goal-setting for the Remote Hearing Intervention, using the Client Oriented Scale of Improvement (COSI; developed by the National Acoustic Laboratories of Australia)

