8.2 Randomisation Procedures

Following participant consent, and confirmation of eligibility at the screening visit (see section 8.1 for pre-treatment assessments), the participant will be allocated a participant trial number and the randomisation procedure described below will be carried out. An independent statistician will generate the randomisation list which will be uploaded to REDCap (an online randomisation database) for online concealed allocation. Participant randomisation will then be undertaken centrally by the coordinating team using REDCap. Participants will be randomised to either the Hearing Intervention or Healthy Ageing Intervention by computer programme on a 1:1 ratio. The randomisation list and the Trial Subject Log will be kept by the trial manager. The audiologist will receive by secure communication the participant's allocation to the Hearing or Healthy Ageing Intervention.

Participants are considered to be enrolled into the trial following: consent, pre-treatment assessments (see section 8.1), confirmation of eligibility, completion of the randomisation process, allocation of

the participant trial number and intervention by the central coordinating team.

The RHI sub-study (during COVID-19) will not be randomised. All participants will be allocated to the RHI.

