9.6 Unblinding (if applicable)

The allocation will be known to the participant, the trial manager, the research audiologist, and the research assistants delivering the intervention and carrying out the outcome assessments. As such we do not expect there to be any need for unblinding.

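### Self-reported baseline measures are taken after open-label randomisation, so they can reflect knowledge of the allocation

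*Protocol*

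**What the plan says.** Under Protocol 8.1, the last eligibility step of the screening visit (V0, day 0) leads straight to allocation: "if individual meets all the inclusion criteria, inclusive of audiometric eligibility criteria, as per section 6.1 and 6.2: randomisation (Aud"). For the hearing arm, the choice of hearing aid type follows at the same visit, and for earmould users "If earmold then take impression at end of visit (Aud"). Appendix 1 agrees, with randomisation marked under visit 0.

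The baseline visit (V1) has the stated aim "Purpose: to gather baseline measures of primary and secondary outcomes" and is timed as "When: Day 0 to 2 weeks after screening (V0) and 1-2 weeks before first intervention visit (V2"). A research assistant conducts it. The end of 8.1 allows delays and sets no latest date. V1 is the first collection of HHIE-S, GDS, SF-36, EQ-5D, four IADL items rated by the assistant, SF-DEM, UCLA Loneliness, the cognitive battery and grip strength. The accelerometer is fitted then, and partner ratings are taken if a partner takes part.

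The trial is open. Section 9.6 states: "The allocation will be known to the participant, the trial manager, the research audiologist, and the research assistants delivering the intervention", and section 5 explains why assessors are not blinded.

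Section 8.2 defines enrolment with this order: "Participants are considered to be enrolled into the trial following: consent, pre-treatment assessments (see section 8.1), confirmation of eligibility", with completion of randomisation listed after these.

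Section 11.6.1 uses the V1 scores to judge whether the randomised groups are comparable at baseline.

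**The concern.** A baseline value is useful in a randomised comparison because the allocation cannot have influenced it. Here the allocation comes first and is open. A person who has just had hearing aids selected may rate hearing handicap, mood or quality of life differently from one who has been told to see the GP. The research assistant rating IADL also knows the arm. Baseline physical activity is recorded between V1 and Session A, when control participants may already know that they are in an arm with a physical activity lesson.

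Two uses are at stake. The table in 11.6.1 could no longer separate chance imbalance from a reaction to allocation. Any later analysis that subtracts or adjusts for a V1 score would carry that reaction into the treatment contrast. Section 11.1 describes the future trial as a larger version of this pilot, modified by lessons learnt, so the visit order may carry over unless it is recorded as one of those lessons.

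**Working it through.** The plan gives no figure on this point. The check is of the order of events, followed by an illustration of size.

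**1. Where V1 can fall.** Inputs from 8.1, 8.3 and Appendix 1: V0 and randomisation on day 0; V1 on days 0 to 14; V1 also 7 to 14 days before V2; V2 (Session A) at week 3-4. Enumerating the days that meet every condition:

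| Reading of week 3-4 | Possible days for V1 |
|---|---|
| days 21-28 | 7 to 14 |
| days 15-28 | 1 to 14 |
| days 14-28 | 0 to 14 |

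No reading puts V1 before randomisation, and on most it falls on a later day. Fourteen days is the planned maximum only, because no cut-off is set.

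**2. What could act on V1.** Aids are fitted at Session B (week 5-6), so V1 precedes treatment in every case. Only knowledge of the allocation can act.

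**3. Which variables in 11.6.1 are exposed.** Of the 14 listed, four are clean: age and sex are fixed, and phoneme score and pure tone average are measured at V0 before allocation. The other ten come from V1. Two of these, ACE-III and grip strength, are performance tests and less exposed. The remaining eight (SF-36, EQ-5D, IADL, SF-DEM, UCLA Loneliness, accelerometry, GDS, HHIE-S) are self-report, assistant-rated or behavioural.

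**4. Size of bias if V1 is used as a baseline.** Let c be the between-arm shift at V1 caused by knowing the allocation, in SD units, and ρ the correlation between baseline and follow-up, with equal SDs at both times and no true effect. Then
- bias of the difference in change scores = −c
- bias of the baseline-adjusted difference = −ρc

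The protocol gives neither c nor ρ. Both are assumed:

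| c | change score | adjusted, ρ = 0.5 | adjusted, ρ = 0.7 |
|---|---|---|---|
| 0.1 | −0.10 | −0.05 | −0.07 |
| 0.2 | −0.20 | −0.10 | −0.14 |
| 0.3 | −0.30 | −0.15 | −0.21 |

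**5. What is not touched.** An unadjusted 6-month difference contains no V1 term. A shift in an arm's mean leaves the SD within that arm unchanged. Even pooling two equal arms at V1, c = 0.2 multiplies the SD by √(1 + 0.2²/4) = √1.01 ≈ 1.005, about 0.5%. The precision figures in 11.3 use only proportions and counts. For example, 80% of 76 gives 71.0 to 89.0, and 70% against 20% with 38 per arm gives 30.7 to 69.3. No V1 score enters them.

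**The case against.** The strongest reply is that nothing this pilot decides depends on V1. The four endpoints guiding progression (randomisation, retention, session completion, difference in hearing aid use) contain no V1 score. The protocol states no change-score or baseline-adjusted analysis. Section 11.3 calls the analyses descriptive, and 11.6.3 speaks of differences in means and proportions across arms. Whether adjustment is planned is a matter for the SAP, which is not shown. All of this stands, and it limits the weight of the point.

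Several stronger readings are tempting but not supported:
- **Biased sizing of the main trial.** A reader might infer that the between-arm estimates and SDs are distorted. Unadjusted 6-month differences and within-arm SDs are not.
- **Every V1 measure affected in everyone.** Performance tests are less exposed than self-report. GDS is not among the 6-month measures in 8.4, so no change score for it is possible.
- **Everyone certainly knows their arm by V1.** Section 9.6 says that participants will know but not when. For the hearing arm, aid selection at V0 makes it a fair inference. For controls, whose intervention overview comes at Session A, it is less certain. Nothing, however, withholds the allocation until V1.
- **A special retention cost.** One loss between V0 and V1 is 1/76 = 1.3 percentage points, but so is any loss after randomisation.
- **A flat contradiction between 8.1 and 8.2.** The opening of 8.2 ties eligibility and the pre-treatment assessments to the screening visit, which fits randomisation at V0. However, 8.1 closes its account of both V0 and V1 by calling them pre-treatment procedures. The result is an ambiguity, not a proven conflict.

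**Conclusion.** The point holds in limited form. Followed as written, the plan collects its self-reported and assistant-rated baseline measures, and baseline accelerometry, after open allocation. Eight of the 14 variables in the 11.6.1 table are open to this, and partner ratings are exposed in the same way outside that table. The comparability table is therefore weaker evidence than its label suggests, and any contrast using these V1 scores as a baseline would be biased by the amounts tabulated above. The documents do not show that a shift occurred, and its size is an assumption throughout. The feasibility conclusions and progression guidance are unaffected. The change is worth making because it is cheap and because the future trial, meant to detect differences in cognitive decline, is to grow out of this design.

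**What to change.** **For any further randomisation, and for the main trial.** Amend 8.1, 8.2 and Appendix 1 so that REDCap releases the allocation only once the V1 battery is complete, with the allocation-dependent audiology steps moved to the next audiologist contact. No new test is needed, and V1 may already fall on day 0. For baseline accelerometry to be pre-allocation as well, its recording period would also have to end before release.

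The costs are in scheduling. Session A may now be delivered by the assistant or the audiologist, and the audiologist would have to attend it in the hearing arm. The interval from impression to fitting shortens. The 6-month visit, counted from randomisation, runs from a later date. The benefit within this pilot is limited: the Summary reports 36 participants randomised with complete data, leaving at most 76 − 36 = 40 places, and the remote sub-study is not randomised.

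**For participants already randomised.** Label V1 values as post-allocation in the 11.6.1 table. Treat only the V0 audiometry and phoneme score, with age and sex, as true pre-randomisation baseline. Show any V1-adjusted estimate beside the unadjusted one. This needs no new data.

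**Wording.** State in 8.2 which pre-treatment assessments precede randomisation, so that 8.1, 8.2 and Appendix 1 give one order.
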